An independent Data Monitoring Committee will be established to protect patient safety by monitoring study outcomes, implementation, and data quality. The committee will consist of expert clinicians, statisticians, and scientists, including Ugandans, in the field of PrEP and family planning delivery in sub-Saharan African settings. The committee will meet via teleconference every 6 months and be charged with the decision to recommend stopping the study early if interim analyses yield any safety concerns. In addition, the committee will provide guidance about results from international studies of PrEP and contraception that may spur Ugandan policy change. Reports from all reviews will be submitted to overseeing institutional review boards and ethics committees.

Informed consent

We will perform paper-based or electronic-based consenting of participants. After we have ensured that participants have read and understood the consent forms, we will ask them to append their signature on a tablet or on paper. Each participant will receive a participant information sheet that they can use for reference. However, any participant who wants their consent form to take home will have it printed and given to them. Using electronic-based consenting will greatly reduce the burden of storing paper-based consent forms.

Risks

Risks for this cohort include side effects from PrEP provided to the young women through the study clinic, DMPA and other contraceptives provided through Ugandan public health clinics according to the national guidelines for contraceptive provision in Uganda, and discomfort associated with blood draws, physical exams, interviews, and HIV counseling and testing. Intensive and ongoing counseling and monitoring of side effects and adverse events limit the risk for participants from the direct study procedures. Women will have three DXA scans during the course of the study and be exposed to radiation during each scan. The effective radiation dose from the DXA procedure, approximately 0.01 millisievert (mSv), is similar to that received during a 5-hour airplane flight. The total dose over these 3 scans will be several orders of magnitude less than the radiation exposure women will have from their natural environments (from sources such as sun, air, food, and soil). Women who become pregnant will not undergo DXA scans.

For clinical data collection, standardized surveys will be used that will include questions on sensitive topics, such as sexual behavior. All participants will be extensively counseled about the risk for HIV transmission with sex unprotected by a condom and/or PrEP and the importance of using condoms consistently and correctly. We expect that the risk of HIV transmission will actually be lower in the proposed novel cohort than the general population of young women due to the careful attention that will be given to counseling women about HIV risk and the provision of PrEP. Study staff will be aware of the potential for confidentiality issues with regards to test results from HIV testing that are part of a participant's study documents. For minors who enroll with parental consent, results of HIV testing will be confidential and not available to the parent or guardian. But the study will stipulate that minors will be encouraged to disclose positive results to a responsible adult, which need not be their legal guardian. Support will be provided for such disclosures.

There is the potential for confidentiality issues with regards to study data. Particularly, since parental consent will be required for some participants under the age of 18, these participants would have to share their choice to participate in a study that will follow their contraceptive and PrEP use choices and collect detailed sexual behavior data, whereas otherwise they may not have chosen to disclose this information. Should there be any psychosocial stress associated with participation in the study, counseling by study staff will be provided, or referral to appropriate mental health professionals will be done. The age of consensual sex is 16 years, and therefore underage sex is not an issue in this protocol.

Benefits

Participants will receive individualized HIV risk-reduction counseling and counseling about pregnancy planning and prevention of unintended pregnancy, access to PrEP medication, contraceptives, and free condoms. In addition, participants may benefit in the future from information learned from this study.

Care for persons identified as HIV positive

Women who become infected with HIV will be referred immediately to HIV care centers and encouraged to initiate antiretrovirals in line with Ugandan national antiretroviral guidelines.

Seroconverters who become pregnant will be referred for prevention of mother to child HIV transmission services.

Treatment for injury

Participants will be asked to inform the clinic staff if they feel they have been injured because of taking part in the study. Injuries may also be identified during laboratory testing, medical histories, and physical examinations. Treatment for adverse events related to study participation will be provided by the treatment clinic. If treatment is required that is beyond the capacity of the clinic, the clinic staff will refer the participant to appropriate services or organizations that can provide care for the injury. The study based at IDI will cover the costs of the referral and treatment costs up to the time the participant is stable or injury is resolved.

Study records

Complete, accurate, and current study records will be maintained and stored in a secure manner throughout the study. Study records include administrative documentation and regulatory documentation as well as documentation related to each participant enrolled in the cohort, including informed consent forms, data forms, notations of all contacts with the participant, and all other source documents.

Confidentiality

Every effort will be made to protect participant privacy and confidentiality to the extent possible. Personal identifying information will be retained at the local study site.

VII. CLINICAL RESEARCH SITE

Site location

The Infectious Disease Institute (IDI)-Kasangati research clinic is part of the Infectious Diseases Institute, Makerere University College of Health Sciences. The facility is located next to Kasangati Health Center IV and has adequate space and equipment for ongoing and planned research studies. The Infectious Diseases Institute training team offers specialized courses in HIV management for health providers in Africa. For this study the focus of the training will be combination HIV prevention services including PrEP.

Clinical facilities

The site has a large training room that can accommodate up to 50 people, 3 clinical rooms, 6 counseling rooms, a pharmacy, a phlebotomy room, a side lab, secure data room with data archive, administrative office space, wireless internet, telephone intercom system, community education offices, and a large waiting area which provide sufficient space for the execution of this study.

Staff

The Principal Investigator is a seasoned HIV/AIDS researcher and trainer, of local and international repute. He will lead the study team to maximize the scientific, ethical integrity of the study and ensure the training provided is of high quality. The study employs in total 3 doctors, 2 nurse counselors, 1 pharmacy technician, 2 laboratory staff and 2 community educators/counselors, 2 data personnel, 4 qualitative research associates as well as support and administrative staff. The respective staff are overseen by a site coordinator, training coordinator and administrator. The study site previously implemented the Partners PrEP Study and the

Partners Demonstration Project. The staff have substantial experience in the use of PrEP and its accompanying supportive services. The staff have been involved in the conduct of protocol specific training, development of outreach materials, and have skills in training of adult learners.

Administrative procedures

All administrative procedures regarding protocol compliance, study coordination, study activation, study monitoring, study records, and use of information and publications will be done according to good clinical practice.

Laboratory considerations

We will as much as possible use the public health laboratory facilities for routine laboratory monitoring. In situations where this is not possible, specimens will be collected and transported to the study collaborating laboratories. All specimen collection, transport, processing, testing, archiving, and results reporting will be conducted in accordance with good clinical and laboratory practice standards. The collaborating laboratories for the research clinic are the MUJHU-IDI Core Laboratory, the Makerere University Walter Reed Laboratory, and the Molecular Biology Laboratory in the Department of Medical Microbiology at Makerere College of Health Sciences. These are well-established labs with extensive experience in supporting clinical trials. External Quality Assurance (EQA) procedures will be followed throughout the study and are overseen by the University of Washington International Clinical Research Center.

VIII. REFERENCES

UNAIDS. The Gap Report. Geneva, Switzerland; 2014.

Food and Drug Administration. Truvada approved to reduce the risk of sexually transmitted HIV in people who are not infected with the virus; 2012 [updated 2012; cited]; Accessed September 12, 2015]. Available from:

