Table 2: Effect of TDF-based PrEP on estimated glomerular filtration rate in HIV-uninfected persons [Mugwanya et al. JAMA Int Med 2015]

	Net mean eGFR decline vs placebo (ml/min/1.73 ²)	
	Randomized TDF-based PrEP agent	
	FTC-TDF	TDF
Women	-1.73; p=0.02	-1.47; p=0.05

Figure 3. Contraceptive method selection by contracepting Ugandan women [Makerere University 2014]

Studies of bone turnover in DMPA users have suggested that the effects of DMPA on the skeleton are at least partially mediated through increased bone turnover, with increases in markers of bone resorption, N-terminal telopeptide of type I collagen (NTX), and bone formation, P1NP. In addition, DMPA reduces estradiol and sex hormone-binding globulin (SHBG) levels, resulting in hypoestrogenism that is often accompanied by amenorrhea and alters the balance of bone resorption and formation yielding impairments in bone mass.^{38, 52-56} Recent studies in animal

[figure not shown]
Table 3: Longitudinal studies of the association between DMPA and BMD loss

Study	Population	Anatomical site	Mean %Δ in BMD -
			DMPA vs Nonhormonal
Clark et al 2004	18-35 year old initiators	Hip	24 months: -5.7 vs <-0.4
		Lumbar spine	24 months: -5.7 vs <-0.4
Berenson et al 2004	18-33 year old initiators	Lumbar spine	24 months: -5.7 vs + 1.8
		Total hip	48 weeks: -1.6 vs 0.6; p<0.001
			240 weeks: -5.2 vs 0.2; p<0.001

models also suggest a role of estrogen to hasten recovery from kidney injury, leading to a hypothesis that subclinical kidney injury could be a consequence of hypoestrogenism.⁵⁷⁻⁵⁹

Thus, as TDF-based PrEP is delivered in settings where DMPA is commonly used, a large number of HIV-uninfected women will be exposed to two agents that are each known to reduce BMD. Their concurrent use may act additively or synergistically through pathways of subclinical kidney injury and/or hypoestrogenism to adversely affect bone health and the risk of future fracture (Figure 4).

Figure 4. Schematic of pathways through which concurrent TDF-based PrEP and DMPA use could impact bone density

Summary of the potential for joint effects of PrEP and DMPA on bone health

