We will use dual energy x-ray absorptiometry (DXA) scans to measure BMD annually at 3 anatomical sites (lumbar spine, total hip, and wrist). Additionally, we will derive the trabecular bone score (TBS), an index of lumbar spine trabecular microarchitecture.

Hypothesis: Relative to women using DMPA only (without tenofovir exposure) and women using PrEP only (without DMPA exposure), women concurrently using TDF-based PrEP and DMPA will have lower bone mass and more disruptions in bone microarchitecture.

2. We will investigate whether young women concurrently using TDF-based PrEP and DMPA experience: 1) higher rates of bone turnover, a direct precursor to bone loss and 2) subclinical kidney injury and hypoestrogenism, markers of two mechanistic pathways between TDF and DMPA use and bone mass

At baseline, 3, 6, 12, and 24 months, we will measure:

- 1) Markers of bone formation and resorption (e.g. NTX, P1NP, serum intact parathyroid hormone, total and bioavailable 25-OH-vitamin D)
- 2) Markers of kidney function (phosphate, glucose, creatinine, total protein, albumin) and
- 3) Markers of estrogen (serum estradiol, sex hormone binding protein, and the occurrence of amenorrhea)

Hypothesis: Relative to women using DMPA only and PrEP only, women concurrently using TDF-based PrEP and DMPA will have increased bone turnover markers and PTH. In addition, women concurrently using TDF-based PrEP and DMPA will have more frequent subclinical kidney injury (relative to women without tenofovir exposure) and reduced serum estrogen (relative to women without DMPA exposure).

3. Using mediation analysis, we will identify the degree to which the pathways through subclinical kidney injury and hypoestrogenism account for changes in bone density among women concurrently using TDF-based PrEP and DMPA

We will conduct mediation analysis to determine the degree to which changes in the pathways through subclinical kidney injury, hypoestrogenism and the combination of these pathways account for changes in bone density.

Hypothesis: The pathway through hypoestrogenism will be a stronger link between concurrent TDF-based PrEP and DMPA use and bone density changes.

Population

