The proposed study will enroll approximately 500 HIV negative Ugandan women ages 16-25. This age group has a high risk for sexual HIV transmission and they also need effective contraceptive options and thus they will be an important part of the study population. Secondly, bone mass is acquired until approximately age 25 and there may be differences in the attainment of peak bone mass if PrEP and DMPA use is started at age 16 with up to 9 years of use prior to reaching peak bone mass versus age 18. Thus, since this research question is of particular importance to younger females and they will benefit most from the information obtained through this study, it is ideal to include them in the study population.

Location

Study visits will take place at the Infectious Disease Institute (IDI)-Kasangati research clinic, located in the Kasangati area of Kampala in close proximity of several public health care facilities. DXA scans will be conducted at the Makerere University-John Hopkins University Research Collaboration clinical site (MUJHU), ~5 km from the IDI-Kasangati research clinic. Women will be transported to MUJHU for scans by study vehicles which has comprehensive insurance that covers bodily injury of all vehicle occupants and third parties and drivers.

Eligibility

Inclusion criteria:

- Age 16-25
 - o If age 16-17:
 - qualification as an emancipated minor (due to past pregnancy, being married, having a child, or catering for their own livelihood) or
 - a mature minor (due to having a sexually transmitted infection) or
 - able to have a parent/guardian provide informed consent
- HIV-uninfected
- Initiated DMPA within the past 90 days or using condoms only for contraception
- Willing and able to provide written informed consent
- Not planning to get pregnant in the next 24 months
- Sexually active
- Planning to remain in the study area for the next 2 years

Exclusion criteria:

- Currently enrolled in a biomedical HIV-1 prevention study
- Current or prior use of PrEP consecutively in the last 3 months
- Abnormal renal function (creatinine clearance <60 min/ml)
- Hepatitis B infection
- Currently pregnant or breastfeeding
- If history of DMPA use, 1) DMPA use of greater than 90 days with last injection within 2 years of enrollment or 2) continuous DMPA use of greater than 2 years duration at any time
- Current use of implant, IUD, or oral contraceptives
- Past hysterectomy, oophorectomy, or tubal ligation

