- Current or recent history of primary or secondary amenorrhea
- Taking medications known to interfere with bone metabolism (steroids, anti-convulsants, bisphosphonates, cancer drugs).
- Has any other condition that would preclude the ability to provide informed consent, make study participation unsafe, complicate the interpretation of study findings or otherwise interfere with achievement of the study objectives, in the investigator's discretion.

Sample size and study power

Power calculations are based on the number of participants needed to achieve aim 1. Our target sample size is 500 women, of which 300 will be using DMPA and 200 will be using condoms for contraception. We calculate that with 300 women newly initiating DMPA and 75% of women choosing to initiate PrEP, thus with 225 women concurrently using PrEP and DMPA and 75 women using DMPA without PrEP, we will have >90% power to detect changes as low as 2.2% in BMD (with 1.0 g/cm² mean BMD loss) at any anatomical site between women using PrEP and DMPA concurrently and women using DMPA only during the 24 month follow up period (Table 4). Should more than 90% of women choose to initiate PrEP (270 women concurrently using PrEP and DMPA and 30 women using DMPA without PrEP), we will have 80% power to detect changes of >2.7% or more and should initiation rates be closer to 50% (150 women concurrently using DMPA and PrEP and 150 women using DMPA without PrEP), we will have >90% power for all comparisons.

Table 4. Power calculations. N=500: 300 on DMPA and 200 on condoms, shown with a range of PrEP acceptance for the primary comparison of DMPA + PrEP vs DMPA ($\alpha=0.05$)

Expected PrEP acceptance	Outcome: BMD (Aim 1)			Outcome: NTX (Aim 2)		
	Mean % Δ (std dev range)	Mean Δ	Power	Mean % Δ	Mean Δ	Power
75% (225 DMPA+PrEP, 75 DMPA)	2.2 (4–5) (0.5–1.0)	0.5 (0.5–1.0)	91%	2.2 (4–5)	0.10 (0.2 – 0.5)	>99%
75% (225 DMPA+PrEP, 75 DMPA)	2.5 (4–5) (0.5–1.0)	0.5 (0.5–1.0)	>96%	2.5 (4–5)	0.20 (0.2 – 0.5)	>96%
75% (225 DMPA+PrEP, 75 DMPA)	3 (4–5) (0.5–1.0)	1.0 (0.5–1.0)	>99%	3 (4–5)	0.50 (0.2 – 0.5)	>99%
90% (270 DMPA+PrEP, 30 PrEP)	2.5 (4–5) (0.5–1.0)	0.5 (0.5–1.0)	74-90%	2.5 (4–5)	0.10 (0.2 – 0.5)	>99%

Recruitment

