Subclinical kidney injury	
 Urine: phosphate, glucose, creatinine, total protein, albumin Serum: phosphate, glucose, creatinine 	eGFR decline calculated using Chronic Kidney Disease Epidemiology equation ($\geq 25\%$ decline from baseline or creatinine clearance $<60 \text{ mL/min}$)	
 Tubular proteinuria: elevated urine protein with urine albumin: protein ratio <0.4, Euglycemic glycosuria, Phosphaturia defined as increased fractional excretion of phosphorus $>15\%$ or maximum rate of tubular phosphate reabsorption to the glomerular filtration rate
Hypoestrogenism	
 Serum estradiol Sex hormone-binding globulin 	Percent change from baseline of serum estradiol with	Frequency of amenorrhea, defined as the absence of menses for at least 3 menstrual cycles

Retention and study exit

Upon completion of study follow up, women will be provided with referrals to clinics of their choice to continue contraceptive and PrEP provision. Since the interim guidelines for HIV prevention now include PrEP, by the time this study is completed, we anticipate that PrEP will be available through public facilities. We will provide participants with information about which facilities are actively providing PrEP and link them to services at that clinic via a referral.

Special circumstances

a. HIV seroconversion

HIV rapid testing will be conducted quarterly during follow up. We expect the rate of HIV seroconversion to be very low, due to the use of PrEP and repeated counseling about HIV prevention and PrEP. However, in the event of HIV positive rapid test results, PrEP will be stopped immediately and additional blood samples will be drawn for confirmatory EIA testing, plasma HIV RNA quantification, drug resistance, and/or drug levels. When with confirmed HIV seroconversion will be extensively counseled and referred to local clinics providing antiretroviral medications and HIV care. At the visit when HIV seroconversion is confirmed, women will be exited from the study once the set of study procedures for an exit visit are completed. HIV seroconverters who are pregnant will be referred for services to prevent mother to child HIV transmission and study staff will go to great lengths to ensure that women experience no delays in accessing these services.

b. Pregnancy

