- 2) proximal tubular injury (tubular proteinuria defined as elevated urine protein with urine albumin-protein ratio < 0.4 , euglycemic glycosuria, phosphaturia defined as increased urinary excretion of phosphorus $> 15\%$ or maximum rate of tubular phosphate reabsorption to the glomerular filtration rate).

These markers were selected because they are routinely available in clinical practice and have been used in prior studies. The cutoff of $\geq 25\%$ for eGFR decline was adapted from established criteria for the diagnosis of acute kidney injury;⁴¹ eGFR decline of this magnitude has been associated with increased morbidity and mortality.²²⁻²⁴

To determine whether young women using PrEP alone or concurrently with DMPA experience higher rates of subclinical kidney injury, we will perform a qualitative comparison of the incidence of individual markers of kidney injury among women using PrEP (alone or concurrently with DMPA) versus women who have no exposure to TDF.

Aim 2, part 3. We will investigate whether young women concurrently using TDF-based PrEP and DMPA experience elevated markers of hypoestrogenism relative to women using DMPA alone

This outcome will be defined as the percent change from baseline serum estradiol over 24 months and we will adjust for sex hormone-binding protein.⁵⁶ The secondary outcome will be based on self-reported missed menses, with > 3 missed menses in a row categorized as amenorrhea.

To determine whether young women concurrently using DMPA alone or concurrently with PrEP experience greater frequency of hypoestrogenism, we will conduct time-dependent logistic

regression among women using DMPA and women not exposed to DMPA, comparing the proportion of visits with hypoestrogenism.

Aim 3. Using mediation analysis, we will identify the degree to which the pathways through subclinical kidney injury and hypoestrogenism account for changes in bone density among women concurrently using TDF-based PrEP and DMPA

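### The amenorrhea exclusion has no look-back period and is not limited to amenorrhea before DMPA, so it can remove DMPA users on an effect of the exposure that Aims 2 and 3 study

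*Protocol*

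**What the plan says.** The inclusion criteria (Study Methods, Eligibility) require that a woman has "Initiated DMPA within the past 90 days or using condoms only for contraception". A separate exclusion limits earlier exposure: "DMPA use of greater than 90 days with last injection within 2 years of enrollment". A DMPA user may therefore have had up to 90 days of the drug when her eligibility is judged.

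The exclusion at issue reads "Current or recent history of primary or secondary amenorrhea". It states no duration and no look-back period, and does not mention when DMPA began. The neighbouring exclusions on PrEP and on past DMPA use do carry time limits. The visit table schedules the menstrual cycle questionnaire at screening and at enrolment.

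The Background treats amenorrhea as a companion of the drug's effect, describing DMPA as lowering estradiol and SHBG, "resulting in hypoestrogenism that is often accompanied by amenorrhea". Amenorrhea then appears as an estrogen marker in Aim 2, as the secondary hypoestrogenism outcome, and as a possible marker of the hypoestrogenism pathway in Aim 3.

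The outcome has two definitions. Table 5 gives "Frequency of amenorrhea, defined as the absence of menses for at least 3 menstrual cycles". The Data Analysis text for Aim 2 part 3 has self-reported missed menses, "with > 3 missed menses in a row categorized as amenorrhea". Neither is linked to the exclusion.

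**The concern.** Excluding women with a pre-existing menstrual disorder is sensible. In condom users the rule does only that. In DMPA users it is applied after exposure may have begun, so it can also screen on a consequence of the exposure, and the selection then differs between DMPA and non-DMPA groups.

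The contrasts at stake are those that set DMPA users against women not using DMPA:

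- Aim 1 comparison 2 (concurrent use versus PrEP only) and comparison 3 (concurrent use versus neither);
- the amenorrhea outcome in Aim 2 part 3, whose stated analysis compares women using DMPA with women not exposed to it;
- the Aim 3 hypoestrogenism pathway, which the protocol expects to be the stronger one.

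**Working it through.** **The plan's own figure.** Table 4 is not in dispute. For 225 versus 75 women, a difference of 2.2 points and SD 5, the standard error is 5 × √(1/225 + 1/75) = 0.667. Then 2.2/0.667 = 3.30 and 3.30 − 1.96 = 1.34, which gives power of 91%, as stated. The exclusion acts before enrolment, so the target numbers and this power do not change.

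**Can drug-related amenorrhea meet the protocol's definitions by the time of enrolment?**

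Inputs from the protocol: window W = 90 days (inclusion criteria); k = 3 missed cycles (Table 5) or k = 4, that is, more than 3 (Data Analysis, Aim 2 part 3).

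Assumptions not in the protocol: cycle length L of 21, 28 or 35 days; injection equally likely on any day of the cycle; enrolment equally likely on any day from 0 to W; every woman stops menstruating at injection. The last assumption makes the results upper bounds for the given enrolment pattern.

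There are two ways to count:

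- A, k full cycles elapsed since injection: (W − kL)/W, or 0 if negative.
- B, the k-th expected menses missed. This falls between (k−1)L and kL days after injection. The share is [W − (k−1)L − L/2]/W when W ≥ kL, and [W − (k−1)L]²/(2WL) when W lies between (k−1)L and kL.

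At L = 28 and W = 90:

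- k = 3: A = (90 − 84)/90 = 6.7%; B = (90 − 56 − 14)/90 = 22%.
- k = 4: A = 0, since 112 days exceeds 90; B = (90 − 84)²/(2 × 90 × 28) = 36/5040 = 0.7%.

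| Cycle length | At least 3 (A to B) | More than 3 (A to B) |
|---|---|---|
| 21 days | 30% to 42% | 6.7% to 18% |
| 28 days | 6.7% to 22% | 0% to 0.7% |
| 35 days | 0% to 6.3% | 0% |

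If all women enrol within 30 days, both definitions give 0%. Even on a 21-day cycle, the third expected menses cannot be missed before day 42.

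**Looser reading by a site.** The exclusion adopts neither definition. Counting as in B at L = 28 and W = 90, two missed menses give (90 − 28 − 14)/90 = 53% and one gives (90 − 14)/90 = 84%. For one missed menses with enrolment within 30 days, the share is (30 − 14)/30 = 53%. These are again ceilings that assume menses stop at once in every woman. They show how much depends on the missing definition and do not predict how many would be excluded.

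**The case against.** Primary and secondary amenorrhea are diagnostic terms, and a site may well read them as a pre-existing disorder. Nothing says that menses missed after an injection count. Ninety days is an outer limit: the study targets new starters, some women start at the study clinic, and the enrolment scan is meant to fall in the first week of the method where feasible. Early enrolment shrinks the problem, and under the Data Analysis definition it nearly vanishes at a 28-day cycle. Requiring women to be free of amenorrhea at entry is also a defensible way to study new onset. All of this limits the extent. It does not remove the gap, because the first-week scan is only an aim, the 90-day criterion stands, and no text exempts amenorrhea that began after injection.

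A reader might infer that the rule discards the strongest DMPA responders and so understates the estradiol fall, the BMD loss and the study's main result. The documents do not support that:

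- The screen is on menses, not estradiol. Women with suppressed estradiol who still menstruate stay in.
- The primary hypoestrogenism outcome is percent change from baseline estradiol. A woman already suppressed at entry has less room to fall, so excluding her could move the estimate either way.
- Comparison 1 (concurrent use versus DMPA only), on which the study is powered, applies the same rule to both groups.
- The protocol gives no frequency of early amenorrhea on DMPA, no distribution of time since injection, and no figure for extra bone loss in women with early amenorrhea. Any BMD bias would rest wholly on assumed inputs.

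**Conclusion.** The point holds as a gap in the eligibility wording. The rule as written can select on an effect of exposure that the protocol itself treats as an outcome and a candidate mediator marker, and it can do so only among DMPA users.

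Its reach depends on enrolment timing and on how sites read the criterion. At a 28-day cycle with even enrolment over 90 days, the ceiling is 6.7% to 22% under Table 5 and 0% to 0.7% under the Data Analysis text. Across cycles of 21 to 35 days it is 0% to 42% and 0% to 18%. Early enrolment lowers these figures; enrolment concentrated near day 90 or a looser reading raises them.

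The concern is confined to Aim 1 comparisons 2 and 3, the amenorrhea outcome of Aim 2 part 3, and the Aim 3 hypoestrogenism pathway. Bias in comparison 1 is not shown, the direction for estradiol change is not established, and the size of any BMD bias cannot be derived. The correction is still worth making because it is cheap and replaces a screen that may follow exposure with one that precedes it.

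**What to change.** - State that for DMPA users the exclusion refers to menstrual status before the first DMPA injection, and for condom users to status at screening. Give it a look-back period.
- Add the question on pre-DMPA menstrual pattern to the existing screening menstrual questionnaire.
- Do not exclude for amenorrhea that began after the injection. Record it as present at entry, so that the amenorrhea and mediation analyses can handle it.
- Reconcile the amenorrhea definitions in Table 5 and in the Data Analysis text for Aim 2 part 3.

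The cost is a short change to the exclusion, one question on an existing form and one aligned definition. There are two drawbacks: DMPA users must recall their earlier cycles over up to 90 days, and some women will enter with the secondary outcome already present.

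### The 80% power for a 2.7% BMD difference was calculated at 90% PrEP uptake, but the protocol claims it for uptake above 90%, where power falls

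*Protocol*

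**What the plan says.** All of this is in the protocol, Section III, under Sample size and study power, and in Table 4 there.

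- Planned size: "Our target sample size is 500 women, of which 300 will be using DMPA and 200 will be using condoms for contraception". The power comparison takes place within the 300 DMPA users.
- Table 4 is headed as power "for the primary comparison of DMPA + PrEP vs DMPA ($\alpha=0.05"). It gives an SD range of 4 to 5 for the percentage change in BMD.
- The planning case is 75% uptake (225 against 75), with 50% (150 against 150) as a low-uptake alternative.
- The high-uptake alternative reads: "Should more than 90% of women choose to initiate PrEP (270 women concurrently using PrEP and DMPA and 30 women using DMPA without PrEP"), followed by "we will have 80% power to detect changes of >2.7% or more".
- The last row of Table 4 labels the same split "90% (270 DMPA+PrEP, 30 PrEP") and gives 74-90% power for a 2.5% difference.

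The section gives no calculation for uptake above 90%.

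**The concern.** The words describe an open-ended range above 90%, while the group sizes in brackets describe its lower edge. With a fixed total of 300, moving above 90% takes women out of the smaller group, which governs the standard error. Power therefore cannot hold at its 90% value across the range.

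This matters because PrEP is offered to every participant (Overall Design). The visit table schedules PrEP counselling at every visit and PrEP provision at enrolment and every visit after it. Very high uptake is the outcome that would empty the DMPA-only group, and this sentence is the only place where the section speaks to it. Anyone checking observed uptake against the sentence would see no loss of power at 95%, with 15 comparators left.

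**Working it through.** **Inputs.** Total DMPA users 300; alpha 0.05; difference 2.7%; SD 4 to 5; group sizes 270 and 30 (all from the sample size section and Table 4). The number of sides is not stated. Two-sided is inferred because it reproduces the protocol's figures.

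**Formula.** For groups n1 and n2, SE = SD × √(1/n1 + 1/n2), and power ≈ Φ(difference/SE − 1.96). The difference detectable with 80% power is (1.960 + 0.842) × SE.

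**Step 1: which uptake was calculated.** 270/300 = 90% exactly.

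**Step 2: reproduce the 80%.** With SD 5, SE = 5 × √(1/270 + 1/30) = 0.962. Then 2.7/0.962 − 1.96 = 0.846, and Φ(0.846) = 80.1% (79.9% with the noncentral t). A one-sided test would give 87.7%, which does not match.

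**Step 3: confirm the method on Table 4.**

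| Split | Difference | SD | Recomputed | Table 4 |
|---|---|---|---|---|
| 225 vs 75 | 2.2% | 5 | 91.0% | 91% |
| 225 vs 75 | 2.5% | 5 | 96.3% | >96% |
| 225 vs 75 | 3% | 5 | 99.5% | >99% |
| 270 vs 30 | 2.5% | 5 to 4 | 73.8% to 90.1% | 74-90% |

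The method and the SD of 5 behind the 80% are thus recovered from the protocol's own numbers.

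**Step 4: move uptake above 90%, keeping 300 women and a 2.7% difference.**

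| Uptake | Split | Power, SD 5 | Power, SD 4.5 | Power, SD 4 | Detectable with 80% power, SD 5 / SD 4 |
|---|---|---|---|---|---|
| 90% | 270 vs 30 | 80.1% | 87.7% | 93.9% | 2.70% / 2.16% |
| 91% | 273 vs 27 | 76.3% | 84.5% | 91.7% | 2.83% / 2.26% |
| 92% | 276 vs 24 | 71.8% | 80.5% | 88.7% | 2.98% / 2.39% |
| 93% | 279 vs 21 | 66.5% | 75.5% | 84.7% | 3.17% / 2.54% |
| 94% | 282 vs 18 | 60.3% | 69.4% | 79.3% | 3.41% / 2.72% |
| 95% | 285 vs 15 | 53.1% | 62.0% | 72.2% | 3.71% / 2.97% |

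Worked line for 95%, SD 5: SE = 5 × √(1/285 + 1/15) = 1.325; 2.7/1.325 − 1.96 = 0.078; Φ = 53.1%; detectable difference 2.802 × 1.325 = 3.71%. Noncentral t values are at most 0.3 percentage points lower throughout.

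**Step 5: below 90%.** At 75% uptake, SE = 5 × √(1/225 + 1/75) = 0.667 and 2.7/0.667 − 1.96 = 2.09, giving 98%. Power for 2.7% is higher at 75% than at 90%, so 90% is an upper limit on uptake for the 80% statement at SD 5.

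**The case against.** The strongest reply is that nothing has been miscalculated. The group sizes stand beside the claim, the table row is labelled 90%, and 270 against 30 does give 80%. That stands: the fault lies in the wording of the range.

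It can also be said that the protocol already discloses the direction of the risk. The detectable difference grows from 2.2% at 75% uptake to 2.7% at 90%, and the last row of Table 4 shows power down to 74% for a 2.5% difference. This also stands, but those figures stop at 90%. They do not show how fast power falls beyond it, which is the range the sentence claims to cover.

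Uptake of 95% is not forecast anywhere in the protocol; the planning value is 75%. The figures at 95% therefore show sensitivity and do not predict the trial's power.

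Finally, the sentence speaks of changes of more than 2.7%, so one could say that it leaves room for larger differences. Read that way it would name no detectable difference at all. The natural reading is that 2.7% is the smallest difference detected with 80% power.

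A reader might go further and infer that 80% power holds only at exactly 90% uptake. The document does not support that without conditions. Power is higher below 90%. Above it, 80% lasts to about 92% uptake at SD 4.5 and to nearly 94% at SD 4, both within the protocol's SD range.

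**Conclusion.** The concern holds as a misstatement of range. The 80% power for a 2.7% difference belongs to 90% uptake at SD 5, and the protocol attaches it to uptake above 90%. At SD 5 the claim fails as soon as uptake passes 90%; at SD 4 it fails at about 94%. At 95% uptake it fails across the protocol's whole SD range.

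This rests on a two-sided 5% comparison of two means, a fixed 300 DMPA users, and no losses, which is the basis that reproduces the protocol's own figures. Any loss from the DMPA-only group would lower power further.

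Two stronger readings are not supported. The power calculation itself is not wrong, and the trial is not shown to be underpowered at its planned 75% uptake. Nor does the last row of Table 4 describe a comparison with PrEP-only women. The caption, the three rows above and the text all identify the 30 as DMPA users without PrEP, so the label is a clerical slip that changes no calculation.

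**What to change.** In the high-uptake sentence, replace more than 90% with 90% and name the SD of 5 behind the 80%. Add one sentence: above 90% uptake, power for a 2.7% difference declines, reaching 53% (SD 5) to 72% (SD 4) at 95% uptake (285 against 15), where the difference detectable with 80% power is 3.7% to 3.0%. Giving both SDs keeps the statement consistent with the range in Table 4. As a minor correction, change the label in the last row of Table 4 to 30 DMPA.

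The cost is one revised sentence, one added sentence and one label. Sample size, design and analysis do not change. The drawback is that the stated power at very high uptake becomes less favourable.
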